11.5 Analysis of Secondary Efficacy Outcomes

The key secondary outcomes will be tested in the following order:

1. Shift analysis of 90 day mRS under proportional odds model across the mRS scale, as described in [Section 11.4](#) above.
2. The NIHSS 0-2 vs. 3 or greater at 90 days.
3. The BI at 95-100 vs. 0-90.
4. The mortality rate at 90 days.
5. The proportion of subjects with mRS score of 0-1 at Day 90.

11.5.1 Modified Rankin Scale – Shift Analysis

The mRS shift analysis will be conducted as described in [Section 11.4](#) above.

11.5.2 National Institutes of Health Stroke Scale

The NIHSS scores will be dichotomized into 0-2 (indicating a good neurological outcome) versus >2 (indicating otherwise). The proportion of subject achieving a good neurological outcome at Day 90 or the last rating in NA-1 versus placebo control subjects will be compared using the same logistic regression model as in the primary efficacy.

11.5.3 Barthel Index

The BI scores will be dichotomized at 0-90 (indicating otherwise) versus 95-100 (indicating independent functioning with activities of daily living). The proportion of subject with independent functioning with activities of daily living at Day 90 in NA-1 versus placebo control subjects will be compared using the same logistic regression model as in the primary efficacy.

11.5.4 Mortality Rate

Mortality rates, as defined as the number of deaths observed divided by the number of subject observed over the 90 day study period between NA-1 and placebo control subjects, will be analyzed by the same logistic regression model as in the primary efficacy.

11.5.5 Modified Rankin Scale – 0-1 Dichotomy Analysis

The mRS scores will also be dichotomized into 0-1 (indicating freedom from disability) and > 1 (indicating otherwise). The proportion of subject with freedom from dependence/disability at Day 90 in NA-1 versus placebo control subjects will be compared using the same logistic regression model as in the primary efficacy.

11.6 Analysis of Tertiary Efficacy Outcomes

11.6.1 EQ-5D-5L

For the EQ-5D-5L, the difference between NA-1 and placebo control subjects in the distribution of the index and VAS scores on these scales at Day 90 will be presented descriptively.

11.6.2 Volume of Stroke

The total volume of new a) DWI and b) FLAIR lesions in NA-1 versus placebo control subjects will be calculated using a linear regression using a cubic root transformation. Total volume will be assessed using a linear regression using a cubic root transformation if needed. An ANCOVA will be fit and summarized.

Specific covariates are listed in [Section 11.7](#).

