These criteria can be met using CT scanning and the data can be gathered and interpreted in <10 minutes. Using the ASPECTS, extensive infarction can be excluded. Using CTA detailed information can be gained on the location of occlusion and the burden of thrombus. Further, the CTA (from arch to vertex) can aid the interventionist in pre-planning navigation from the aortic arch to the thrombus. The pattern of collaterals is also discernible from CTA; patients with absent or very poor collaterals do not benefit from therapy, simply because it cannot be brought to bear in a timely enough fashion to prevent significant infarction. In ESCAPE³, slightly more than half of patients were imaged using multi-phase CTA. Single-phase CTA and dynamic/multiphase CTA were used to select patients in the remaining cases. Many sites had access to CTP imaging but did not use it for patient selection. However, the pattern of collateral circulation can be assessed using CTP imaging.

Thus, a fast image acquisition “good scan (small core), proximal occlusion, adequate collaterals” model of patient selection is being adopted. This group of patients has shown a large treatment effect of endovascular therapy. This group of patients represents the near ideal “ischemia-reperfusion” paradigm. Thus we propose that it is the best subset of stroke patients in which to test the benefits of neuroprotection.

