7 SELECTION AND WITHDRAWAL OF SUBJECTS

7.1 Study Enrolment Process

Subjects will be identified using usual standard of care screening methods at the acute stroke hospital. This will include screening by neurology residents, fellows, nurse practitioners, physician assistants or faculty physicians.

Sites will only be selected to participate in the study if they have established mechanisms for screening this population of subject. This includes standard of care use of NCCT and CTA.

All subjects will undergo an acute clinical assessment, blood laboratory assessment and baseline brain imaging. For the standardization of the imaging criteria for patient selection across sites, all sites will perform a NCCT brain and CTA to determine patient eligibility. The NCCT head will be assessed using ASPECTS (Alberta Stroke Program Early CT Score) prior to randomization. Patients with an ASPECTS score of 5 or greater may be included in the study. ASPECTS is a reliable and reproducible assessment tool with low inter- and intra-observer variability²² and is used to standardize the imaging criteria used for patient selection. The CTA will be also assessed for collateral status using a collaterals scoring system similar to that used for patient selection in the ESCAPE trial. Instructions for the determination of the ASPECTS score and collaterals scoring on CTA are provided in [Appendix 2: Derivation of ASPECTS on NCCT and Collaterals Scoring on CTA](#) and additional details can be found at www.aspectsinstroke.com.

From the perspective of imaging to recanalization and other interval times, the first slice of the baseline NCCT is when the timing begins.

If CTP is done routinely at the site, NCCT and CTA must still be used to determine inclusion criteria. It is mandated that a CTP cannot be performed before the CTA.

In order to track the potential for enrolment, each enrolling site will provide the total number of patients admitted to that site with the diagnosis of AIS. Individual patient screening logs will not be required.

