11 STATISTICS

11.1 Sample Size Considerations

Assuming a 52% overall responder rate for the placebo group, there will be an approximately 80% power to detect an 8.7% absolute effect difference between response rate (proportion of responders, with Day 90 mRS in the range 0 to 2) with NA-1 and placebo, at alpha level 0.05, 2-sided with a planned sample size of 1076 evaluable subjects, randomized 1:1, per group, accounting for a single interim analysis when 600 subject have reached their primary endpoint assessments, with O'Brien-Fleming alpha-spending function (EaST® V6.3) stopping boundary for overwhelming efficacy and a non-binding 1% conditional power futility stopping boundary. The sample size will be inflated approximately 4% to N= 560 per group to account for loss-to-follow-up and drop-outs.

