11.7 Adjustment for Covariates and Subgroup Analyses

In addition to the primary and secondary analyses adjusting for age, sex, baseline NIHSS score, baseline ASPECTS score, occlusion location, intravenous alteplase use, declared first endovascular device and site, exploratory analyses will be conducted to determine the potential roles of common baseline characteristics and assess potential heterogeneity of treatment effect across subgroups. Specific subgroups of interest include the very elderly (age > 80 years), men vs. women, subject with different baseline stroke severity (on NIHSS and measured radiologically on ASPECTS), subject treated with intravenous alteplase (yes/no), declared first endovascular approach, baseline occlusion location (MCA vs. ICA), and subject with long/short time from onset to treatment. Full details will be specified in detail in the SAP.

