Secondary	Day-90 mRS	Ordinal (0-4,5+6)	ITT	mRS cumulative logits modeled as a function of treatment, baseline ASPECTS, occlusion location, age, sex, baseline NIHSS, alteplase*thromb_app, study site
	Day-90 NIHSS	Binary (≤ 2 vs. > 2)	ITT	logit(binary NIHSS) modeled as a function of treatment, baseline ASPECTS, occlusion location, age, sex, baseline NIHSS, alteplase*thromb_app, study site
	Day-90 Barthel	Binary (< 95 vs. ≥ 95)	ITT	logit(binary Barthel Index) modeled as a function of treatment, baseline ASPECTS, occlusion location, age, sex, baseline NIHSS, alteplase*thromb_app, study site
	Day-90 Mortality	Binary day-90 death status	ITT	logit(binary death status) modeled as a function of treatment, baseline ASPECT, occlusion location, age, sex, baseline NIHSS, alteplase*thromb_app, study site
	Day-90 mRS	mRS Binary (≤ 1 vs. > 1)	ITT	logit(binary mRS) modeled as a function of treatment, baseline ASPECTS, occlusion location, age, sex, baseline NIHSS, alteplase*thromb_app, study site
Tertiary	EQ-VAS	0-100	ITT	EQ-VAS modeled as functions of treatment, baseline ASPECTS, occlusion location, age, sex, baseline NIHSS, alteplase*thromb_app, study site
	Stroke volume	continuous	ITT	Stroke volume (or cubic root transformation of stroke volume) modeled as a function of treatment, baseline ASPECTS, occlusion location, age, sex, baseline NIHSS, alteplase*thromb_app, study site
	BNT15	0-15	ITT	BNT15 Score modeled as a function of treatment, baseline ASPECTS, occlusion location, age, sex, baseline NIHSS, alteplase*thromb_app, study site
	SNAP	0-100	ITT	Total SNAP Score modeled as a function of treatment, baseline ASPECTS, occlusion location, age, sex, baseline NIHSS, alteplase*thromb_app, study site
	MoCA	Binary (< 26 vs. ≥ 26)	ITT	logit(binary MoCA) modeled as a function of treatment, baseline ASPECTS, occlusion location, age, sex, baseline NIHSS, alteplase*thromb_app, study site
	Day-30 mRS	Binary (≤ 2 vs. > 2)	ITT	logit(binary mRS) modeled as a function of treatment, baseline ASPECTS, occlusion location, age, sex, baseline NIHSS, alteplase*thromb_app, study site
Exploratory	Day-90 mRS	Binary (≤ 2 vs. > 2)	ITT	Separate logistic regression models in which the logit(binary mRS) is modeled as a function of treatment only, by each of the subgroups to be considered in the Subgroup forest plots

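### The exploratory infarct-volume ANCOVA leaves out onset-to-randomization time and baseline collateral status: a possible, probably modest, loss of precision without bias

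*Protocol*

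**What the plan says.** Infarct volume on 24-hour imaging is a tertiary outcome. Protocol 11.6.2 plans a linear regression, with a cube-root transformation if needed, and states "An ANCOVA will be fit and summarized". It refers to Section 11.7 for the covariates: age, sex, baseline NIHSS, "baseline ASPECTS score, occlusion location, intravenous alteplase use, declared first endovascular device and site". SAP 7.3.2 fits the model in the same way as the EQ-VAS model, which itself borrows the covariates of the primary and secondary analyses. SAP Table 2 gives the row in full: "Stroke volume (or cubic root transformation of stroke volume) modeled as a function of treatment", then ASPECTS, occlusion location, age, sex, NIHSS, the alteplase-by-device strata and site.

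These are the stratification and minimization variables. Time since onset and collateral status are not among them, although both are established before randomization:

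- **Time.** Protocol 7.2 requires randomization within 12 hours of last-seen-well. Protocol 6.2 sends the server's randomization time to the central database.
- **Collaterals.** Protocol 7.1 says "The CTA will be also assessed for collateral status using a collaterals scoring system". The scale in Appendix 2 runs from 0 to 5, and Protocol 7.3 excludes scores 0 and 1.

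On relevance, Protocol 4.8 says that "patients with absent or very poor collaterals do not benefit from therapy", because treatment cannot reach them in time to prevent substantial infarction. Protocol 4.2 refers in general terms to the fast course of irreversible injury.

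**The concern.** The adjustment set was chosen to balance and analyze 90-day disability. It was then carried over unchanged to a tissue outcome for which elapsed time and collateral supply are natural predictors. In a linear model, a baseline variable that predicts the outcome beyond the covariates already present reduces residual variance. Leaving it out makes the confidence interval for the NA-1 effect wider than it need be.

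Reducing infarct volume is a stated tertiary objective (Protocol 5.3), and it is the outcome closest to the proposed action of holding the core in check until reperfusion (Protocol 4.7). At stake is the sharpness of that one comparison. Timing also matters. Volumes are read only after database lock (Protocol 8.12, SAP 7.3.2) and unblinding follows lock (SAP 4.0), so covariates added after unblinding would look chosen after the fact.

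**Working it through.** **1. The plan's own figure.** No SD, effect size, power or precision is stated for volume. The only design calculation concerns the primary endpoint: "Assuming a 52% overall responder rate for the placebo group", "an 8.7% absolute effect difference between response rate", "at alpha level 0.05, 2-sided with a planned sample size of 1076 evaluable subjects, randomized 1:1, per group". The 1076 is read as a total (538 per arm), because 2 × 560 = 1120 and 1120/1076 = 1.041, the stated inflation of about 4%.

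- SE under the null (pooled rate 0.5635): √(2 × 0.5635 × 0.4365/538) = 0.03024.
- SE under the alternative: √((0.52 × 0.48 + 0.607 × 0.393)/538) = 0.03012.
- Fixed-design power: Φ((0.087 − 1.960 × 0.03024)/0.03012) = Φ(0.921) = 82.1%.
- With one O'Brien-Fleming-type look at 600/1076 = 55.8% information: 81.8% (pooled variance), against 81.7% in SAP 1.4.
- One-sided boundaries: 0.0027 and 0.0241, against 0.003 and 0.024 in SAP 3.0.

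The primary design reproduces, but it gives no information about the variance of infarct volume.

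**2. Precision of the volume comparison.** Let r be the share of residual variance, after the planned covariates, that the two added variables explain together. Under randomization the variance of the treatment estimate is multiplied by 1 − r. The SE ratio is then √(1 − r) and the equivalent gain in subjects is 1/(1 − r) − 1. No document fixes r, so the range is an assumption and starts at zero.

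| r (assumed) | SE ratio | SE falls by | Equivalent gain in subjects |
|---|---|---|---|
| 0 | 1.0000 | 0% | 0% |
| 0.01 | 0.9950 | 0.5% | 1.0% |
| 0.02 | 0.9899 | 1.0% | 2.0% |
| 0.05 | 0.9747 | 2.5% | 5.3% |
| 0.10 | 0.9487 | 5.1% | 11.1% |
| 0.15 | 0.9220 | 7.8% | 17.6% |

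**3. Cost in degrees of freedom.** Assume 1076 subjects with a volume and about 60 model degrees of freedom, which leaves 1076 − 60 − 1 = 1015.

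- Two extra terms (linear score plus time): variance × 1015/1013 = 1.0020.
- Four extra terms (score as four levels plus time): variance × 1015/1011 = 1.0040.
- Break-even: r = 1 − 1013/1015 = 0.0020 or r = 1 − 1011/1015 = 0.0039.
- A separate category for missing scores costs one more term, about 1/1015 = 0.1% of variance.

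**4. Are the variables available?**

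- *Time:* yes. It is an inclusion criterion, the randomization time is stored automatically, and Protocol 6.7 follows onset-to-infusion time from CRF data.
- *Collaterals:* assessed, but not shown to be stored as a number. The score is not among the locked randomization variables (Protocol 6.2) or the baseline characteristics named in SAP 6.4, although that list is not exhaustive. The core lab reviews images for eligibility, reperfusion, quality and safety (Protocol 8.12). The documents do not say whether it records a 0-5 score.

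**5. Do the documents show that they predict volume?** Only in part. The collateral sentence in Protocol 4.8 describes patients whom Protocol 7.3 excludes. Enrolled scores 2-5 still span the intermediate and good categories of Appendix 2. For time, there is the general remark in Protocol 4.2 and a primate permanent-occlusion experiment in which lesion volume grew over time in both groups (Protocol 4.3.1.3). Nothing addresses how much either variable adds once ASPECTS, NIHSS and occlusion location are in the model.

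**The case against.** The strongest reply is that there is no defect here. Adjusting every endpoint for the stratification and minimization variables is a standard, fully specified choice. The set already holds ASPECTS, which measures baseline infarct extent on imaging, together with NIHSS and occlusion location. Eligibility narrows what is left to explain, because even late presenters must have ASPECTS of at least 5 and collaterals of at least 2. Volume is exploratory, Protocol 6.1.3 speaks of describing tertiary outcomes, and no precision target is missed. Missing collateral scores could remove subjects from a complete-case model and cancel a small gain.

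Most of this stands. It makes a small r plausible and is why the range must begin at zero. It does not show that the addition is worthless: the cost is recovered once r exceeds about 0.002 to 0.004, and the time variable needs no new data.

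A reader might infer four stronger things, none of which the documents support:

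- **That the volume comparison is biased.** Allocation is randomized, so omitting a baseline predictor affects precision only.
- **That the protocol itself names these variables as determinants of volume in enrolled patients.** Its collateral text concerns excluded patients, and its remark on time is general.
- **That a numeric collateral score, or a core-lab reading of it, is ready for analysis.** No section says so. If none exists, obtaining one would mean new readings of about 1120 scans.
- **That power would rise by a known amount.** No power is stated for volume, so there is no starting point from which to measure a rise.

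**Conclusion.** The point holds as an optional improvement to an exploratory analysis. The volume model reuses the mRS covariates and omits onset-to-randomization time, which is available for all subjects, and collateral status, which is assessed for all at baseline. The consequence is a possible loss of precision. Over an assumed r of 0 to 0.15 the standard error could be 0 to 7.8% smaller, and the lower part of that range is plausible given what is already adjusted for. The size rests wholly on this assumed r. The cost figure rests on the assumed 1076 subjects and about 60 model degrees of freedom. The primary analysis, the alpha allocation and the sample size are unaffected.

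**What to change.** Before unblinding, amend SAP 7.3.2 and the stroke-volume row of SAP Table 2 as follows:

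- Add time from last-seen-well to randomization as a continuous covariate. Do not use onset-to-treatment time, as in the SAP 7.4 subgroups, because it includes an interval after randomization.
- Add the baseline collateral score if a recorded score (site or core lab) already exists. Name the source, and use a missing category or a simple imputation from baseline data so that no subject is dropped. If no score is recorded, add time alone.
- Keep the current model as a sensitivity analysis.

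Protocol 11.6.4 leaves the details of tertiary methods to the SAP, to be finalized before the first IDMC meeting. If that date has passed, a dated SAP amendment should record that the change was made before unblinding and that it extends the list in Protocol 11.7 for this outcome only. The cost is a short SAP edit and a few model terms. The time covariate needs no new data, and the collateral score is added only where it has already been recorded.

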11.6.3 Cognitive outcomes

These will be explored using the BNT15, SNAP and the MoCA.

11.6.4 mRS at 30 Days

The overall proportion subjects experiencing a favorable functional outcome 30-days post-randomization, defined as 0 to 2 on the mRS.

The tertiary and all other analyses will be considered exploratory. Details of the methods of analysis will be finalized in the SAP prior to the first IDMC meeting.

11.6.5 Pharmacokinetics

Descriptive statistics will be calculated for plasma concentrations and for all PK parameters (NA-1). In addition, dose proportionality and linearity of dose dependent PK parameters will be investigated. Individual and mean plasma concentration versus time curves will be plotted on linear and semi-logarithmic scales. Plasma concentration versus time curves will be labelled appropriately with treatment regimen and batch number.

11.7 Adjustment for Covariates and Subgroup Analyses

In addition to the primary and secondary analyses adjusting for age, sex, baseline NIHSS score, baseline ASPECTS score, occlusion location, intravenous alteplase use, declared first endovascular device and site, exploratory analyses will be conducted to determine the potential roles of common baseline characteristics and assess potential heterogeneity of treatment effect across subgroups. Specific subgroups of interest include the very elderly (age > 80 years), men vs. women, subject with different baseline stroke severity (on NIHSS and measured radiologically on ASPECTS), subject treated with intravenous alteplase (yes/no), declared first endovascular approach, baseline occlusion location (MCA vs. ICA), and subject with long/short time from onset to treatment. Full details will be specified in detail in the SAP.

11.8 Handling of Missing, Unused and Spurious Data

Every effort will be made to keep missing data, particularly the Day 90 outcome assessments, to a minimum. However, some missing data may be inevitable due to, for example, loss to follow-up. This was kept to a minimum of 1.3% in the ESCAPE trial³. Deceased subject will score 6 on the mRS and be counted as non-responders. For the primary analysis for regulatory submission, we will assume that subject missing the primary endpoint data will be considered to be non-responders. Sensitivity analyses using various imputation techniques will be specified prospectively in the SAP before the database lock for the interim analysis if more than 5% of subject randomized are missing the primary endpoint.

11.9 Analyses of Safety

The safety population will consist of all subjects who received any dose of study drug. The main analyses will be frequency of SAEs and 90-day mortality. It is expected that the safety population and the ITT population will be near-identical.

11.9.1 SAEs

SAEs over the 90-day study period will be summarized by presenting, for each treatment group, the number and percentage of subjects having at least one SAE, having an SAE in each body

system and preferred term, by severity and relatedness to study medication. The frequencies and incidences of SAEs occurring in subjects in the drug and placebo control groups will be summarized within treatment group by the Medical Dictionary for Regulatory Activities (MedDRA) System Organ Class (SOC). The frequencies and incidences of SAEs and discontinuations due to SAEs occurring in subjects in the NA-1 and placebo control groups will be summarized within treatment group.

11.9.2 Mortality

Event rate (%) for mortality over the 90-day study period between NA-1 and placebo control subjects will be compared by logistic regression. The logistic regression model will include factors for treatment group. All deaths will be provided in a listing.

11.9.3 AEs

Additional analyses will consider the frequency of AEs and discontinuations due to AEs. AEs will be summarized by presenting, for each treatment group, the number and percentage of subjects having any AE, having an AE in each body system and preferred term. Severity and relatedness to study medication will be recorded according to [Table 10-1](#). The frequencies and incidences of AEs occurring in subjects in the drug and placebo control groups will be summarized within treatment group by the Medical Dictionary for Regulatory Activities (MedDRA) System Organ Class (SOC).

11.9.4 Vital Signs

Absolute values and changes for vital signs from pre-dose to Day 5 or discharge will be documented. The maximum deviation of BP from Baseline between drug and placebo control groups (systolic and diastolic) to 24 Hours will be analyzed using ANCOVA, including factors for treatment group.

